The primary purpose of this study is to assess the efficacy of larval debridement therapy (LDT) with bagged, sterilized, live, medicinal blow fly (*Lucilia sericata*) larvae (or "BioBags") versus bedside sharp debridement in removing harmful bacteria, biofilm and necrotic tissue from chronic wounds to promote wound healing. Characteristics associated with chronic wound environments will be evaluated through analysis of samples of tissue taken from wound beds before and after both types of debridement. One hundred and forty patients \geq 21 years of age with an open, full thickness wound which is healing by secondary intention (of greater than 8 weeks duration and requires debridement) will be invited to participate. This recruitment number accounts for estimated 10% attrition rate, so final sample number is anticipated to be 128 subjects (64 in each arm). Samples of wound bed tissue and slough tissue (if present) will be collected on Days 0, 4 and 8 or prior to and after each larval debridement intervention or sharp debridement (control). Photos will be taken of the wound bed on Days 0, 4 and 8 or just prior to and after each debridement method. A randomized sampling procedure will place individuals into one of two groups: The intervention group will receive larval debridement therapy once every 4 days for 2 applications (with saline moistened gauze as cover dressing changed daily) and the control group will receive sharp debridement therapy every 7 days for 2 debridements (with wound gel dressing changed daily).

The wound and wound environment will be characterized by assessing wound Matrix Metalloproteinases (MMPs), inflammatory cytokines and the presence of total bacteria, planktonic (free floating) bacteria, and biofilm (sessile) bacteria. Clinicians will be asked to grade the amount of non-viable tissue apparent in the wound bed, appearance of any signs of infection and overall visual appearance of the wound at each visit. Wound size will also be assessed. Subjects will be asked to rate their wound related pain level at each visit before and after the debridement method is applied. Subjects, caregivers and clinicians will be asked to complete a short survey to self-report their perceptions of each method of debridement. Data will be analyzed using bivariate and multivariate methods.

4. **Background:**

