To compare the clinical effectiveness of a self-contained bagged larval debridement therapy (intervention) (BioBag) with bedside sharp debridement (control). The following comparisons will be made: 1) The visual reduction of non-viable tissue in the wound bed of chronic full-thickness lower extremity or diabetic foot ulcers, and 2) The reduction in colony forming units (CFU) of bacterial biofilm in samples taken from the wound bed.

Specific Aim 2

To compare wound characteristics (e.g., inflammatory markers, wound size) in the intervention group (BioBag therapy) and control group (Sharp debridement) over time.

Specific Aim 3

To investigate patient, caregiver and clinician perceptions of larval therapy dressings and bedside sharp debridement using measures of self-reported aesthetics, ease of use, and wound pain.

6. Research Plan:

Research design and methods

Design: A repeated measures, randomized control trial experimental design will be used for this study. Subjects will serve as their own control, in addition to a control group. Initial wound samples will be followed by two subsequent repeated wound samplings approximately four days apart. Informed consent will be obtained prior to all procedures, photo consents will also be obtained for wound photos.

Veteran Site: North Florida South Georgia Veterans Health System

Setting, Sample: A target goal final sample size of one hundred twenty eight adults from the North Florida South Georgia VHS will be recruited (total recruited number anticipated to be ~140 allowing for 10% attrition). Including target of 128 Caregivers and 6 Providers, and accounting for 12 caregivers lost to follow up or 10 subjects who fail screening, the total study recruitment population is 296. Wound providers and clinicians who care for lower extremity or diabetic foot ulcers will be provided with a "Provider Study Flyer" which gives a brief description of the study with inclusion/exclusion criteria listed (to remind the Provider to approach potentially eligible patients with Research Team Contact

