information). The clinicians will also be asked to make a Recruitment Brochure available to potentially eligible patients (those with lower extremity or diabetic foot ulcers over 8 weeks duration). In addition, study flyers will be sent to select VA wound and podiatry offices in the NF/SG VHS. Providers will be asked to contact study team if any patient is willing to hear about the study. If the patient is willing to hear about the study, they may contact a study team member from the contact number on the recruitment brochure or the provider can let the patient know when the research team member is scheduled to be in the provider clinic office and the patient may talk directly to the research study team member for more information. If patients call a research team member, they will have their questions answered but will not be screened over the phone. They will be scheduled to come into the provider office to discuss the study with a research team member and review informed consent. Members of the research study team will review the informed consent with the patient and enroll the subject if they agree to participate. Wound clinicians will not be asked to consent subjects, or to provide a list of patients or appointment times to research team. However, the subject's wound providers (clinicians) will be the ones to perform the sample collection and apply the LDT or bedside sharp debridement. The sample also includes one available caregiver of the patient (non-professional) to answer the caregiver surveys if willing, and the wound care providers, who will be asked to answer the clinician survey regarding perceptions of debridement methods.

Sample Size Power Analysis: Power analysis is based on the patient sample and the primary study aim of comparing debridement methods on clinical effectiveness. The POWER procedure in SAS version 9.2 (Cary, N.C.) was used to conduct the power analysis. Assuming a Type I error rate of .05 and two-sided testing, a sample of 64 is needed in each group to detect a medium effect size of .50 with at least 80% power. This magnitude of effect is considered clinically significant.

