Larval Debridement Therapy (intervention) group: Briefly, wounds may be rinsed with saline and blotted with sterile gauze prior to collecting baseline wound samples at Day 0. Wound measurements and wound photos will be taken at baseline and Day 8. Wound samples will be collected on Day 0, Day 4, and Day 8. One BioBag (larval debridement therapy) will be applied to wound on Day 0 after baseline wound samples are obtained, and this will be removed on Day 4, at which time 2nd wound sample is obtained. Immediately after 2nd wound sample obtained, the 2nd BioBag will be applied. The dead larvae from the Biobags after removal from the subjects in this study will be placed in a sterile container and labeled with study subject number and "1st" or "2nd application." These specimens will be frozen in our VA research laboratory for a future secondary analysis. This will be the subject of a new grant proposal being submitted by the current investigators in 2015 with the aim of examining the digestive track and body of the larvae for the presence of bacteria and correlating this with the bacteria identified in the bacterial analysis of the subject wounds. Size of the Biobag is determined by the size of the wound (typically 5 to 8 larvae per cm² or 50 to 400 larvae per single Biobag). Only cover dressing (saline moistened gauze + dry gauze/secondary cover) will be changed over BioBag on days 1,2,3,5,6, and 7. Last wound sampling (3rd) will be done on Day 8, after 2nd BioBag is removed. Clinicians as well as Veteran participants and non-Veteran participants (at NFRMC) and their caregivers will be given copies of LDT instructions for use (Appendix A/Appendix B). Wound samples will be obtained at each

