sampling date by sterile swab(s) and 3-4mm curette scraping of wound bed using a sterile curette sweeping z track method across wound bed. Sterile filter paper or micropipette/capillary tube may also be used to collect wound fluid. Wound samples will be collected at wound provider's office/clinic and placed in appropriate receptacle (sterile transport tubes with caps or vials with caps) for transport. The sample receptacles will be labeled with assigned subject number, number of visit (1, 2, 3, etc.), date of sample collection, duration and location of wound. Labeled samples will be placed in sealed biohazard bag, then in a biohazard marked cooler with a cold pack, and this container will be placed in a larger transport container for transport to the VA laboratory. Clinicians and clinic staff will be asked to complete sample collection training and biohazard shipping (if shipping is deemed necessary) training before collecting or shipping any wound samples to standardize the procedures and be in compliance with research, safety and shipping regulations. Clinicians will be asked to view a LDT training video before performing application of Larvae in order to further standardize the application.

[figure not shown]
Sharp Debridement Therapy (control) group: Briefly, wounds may be rinsed with saline and blotted with sterile gauze prior to collecting baseline wound samples at Day 0. Wound measurements and wound photos will be taken on Day 0, Day 4, Day 7 (before and after sharp debridement) and on Day 8. Wound samples will be obtained on Day 0, Day 4, and Day 8. Sharp debridement will be performed by patient's wound clinician using standard technique on day 0 after baseline wound measures are obtained and again on day 7. Wound samples will be obtained by sterile swab(s) and 3-4mm curette scraping of wound bed using a sterile curette sweeping z track method across wound bed. Sterile filter paper or micropipette/capillary tube may also be used to collect wound fluid. Wound samples will be placed in appropriate receptacle for transport as described above. Wound gel dressing (with gauze as secondary cover) will be applied to wound after debridement and changed daily as a control dressing. The following depicts the anticipated sampling timeframe for each participant.

LDT group (X denotes sampling procedure)

- Day 0 - **X** pre-measures (**sample 1**); surveys; photos
Apply larvae bag 1
- Day 4 - Remove larvae bag 1

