X post-measure (**sample 2**); Pain survey; photos
Apply larvae bag 2
- Day 8 - **X** final measures (**sample 3**); surveys; photos

SD group

- Day 0 - **X** pre-measures (**sample 1**); surveys; photos
Sharp Debridement 1
- Day 4 - **X** post measures (**sample 2**); pain survey; Wound photos
- Day 7 - Sharp debridement 2 & photos
- Day 8 - **X** final measures (**sample 3**); surveys; photos

Data Collection & Data Management

Measurement of bacterial colonization. A microbiological assessment of the wound samples will be performed. Samples will be measured for both planktonic (single) bacteria and biofilm bacteria by standard clinical microbiology techniques with serial dilution and plating on complete agar medium

plates. Colony forming units (CFUs) will be measured after approximately 24 hours of culture under standard laboratory conditions. Levels of planktonic bacteria and biofilm bacteria will be compared within each sample and chronologically within each patient. Photos will be reviewed by blinded wound clinicians and rated on amount of necrotic tissue present visually in wound bed at each sampling time (reported on scale 0 – 10 based on 0%, 1 = 10% or less, etc.). Data collected from human subject's electronic health record will include characteristics such as wound etiology, wound location/duration, wound treatments, wound photos, wound progress notes, age, gender, comorbid conditions, pertinent laboratory values and medical history. This data will be conducted only by trained research team members designated in the IRB approved study protocol over the duration of the study.

Only de-identified pertinent information per subject sample such as age of subject, visit number (Day 0, 4, 8), location of wound, duration of wound, co-morbid conditions, medications and current wound treatments will be shared with the investigational laboratories or their personnel. Only the PI, site PI, Co-Investigators, and study coordinator(s) will have access to the subject PHI and study folders. UF lab has agreed to destroy any remaining samples at the conclusion of the current study.

Measurement of MMPs. Using techniques such as ELISA or fluorescence resonance energy transfer (FRET) assay methodology, the levels of active MMPs (or measures of MMP activity) will be calculated and expressed as pg/ml of wound fluid and pg/mg protein.

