Measurement of IL6. Using techniques such as ELISA and fluorescence resonance energy transfer (FRET) assay methodology, the levels of active IL6 will be calculated and reported.

Methods for Data Collection & Data Management

Variable	Significance	Sampling time	Source	Specific Aim
Age	Demographic	Baseline	EHR	n/a
ABI	Exclusion criterion	Baseline - enrollment	ABI done after ICF	n/a
% nonviable wound tissue	Appearance of wound bed	Baseline Day 0 and Day 8	Provider assessment	Aim 1
Quantitative Cultures (planktonic and biofilm)	Microbial identification	Day 0 (pre-test), + Day 4 and Day 8	Wound samples	Aim 1
Wound Size in cm ² (volume: L x W x D)	Descriptive	Baseline Day 0 and Day 8	Wound measurements	Aim 2
Interleukin 6	Marker of inflammation	Day 0 (pre-test), + Day 4 and Day 8	Wound sample (fluid and/or tissue)	Aim 2
Matrix metalloproteinases (MMP-2 and 9 equivalent)	Elevated MMPs associated with non-healing wounds	Day 0 (pre-test), + Day 4 and Day 8	Wound sample (fluid and/or tissue)	Aim 2
Perceptions of therapy	Perceptions of debridement	Day 0 (pre-test) + Day 8	Patient, Caregiver & Clinician Surveys	Aim 3

Survey Methods

Subjects will be asked to complete a paper survey at Day 0, Day 4 and Day 8 of the study, querying the patient's perceptions of: wound pain, satisfaction with most recent/current wound care method, ease of

care, effectiveness of most recent wound treatment, aesthetics of current wound treatment and toward sharp debridement and maggots for wound care.

Caregivers and wound clinical providers will be asked to complete a paper survey at Day 0 and Day 8 of the study (if wound clinician is caring for more than one study subject, they will be asked to complete a survey at day 0 of first subject, day 8 of first subject and 3 months later or at completion of the study for each type of debridement), querying them about their perceptions of what the patient's experience was regarding the most recent wound debridement methods as well as satisfaction with most recent/current wound care method, ease of care, effectiveness of most recent wound treatment, aesthetics of most current wound treatment and toward sharp debridement and maggots for wound care.

Data Analysis

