Data will be summarized with descriptive statistics. Data will be checked for implausible values, missingness, and distributional form. Data transformations will be made as necessary to achieve normality. To address Specific Aim 1 (comparing the clinical effectiveness of a self-contained larval debridement therapy with a bedside sharp debridement therapy), the numeric outcome measures of changes (post minus pre) in percent of non-viable tissue and bacterial biofilm will be analyzed using independent samples t-tests. To address Specific Aim 2 (comparing wound characteristics of larval debridement and bedside sharp debridement therapies) over time, longitudinal generalized mixed models (GLMMs) will be used with the dependent repeated measures being wound characteristics (e.g., inflammatory markers, wound size) and the independent variable of group assignment (larval versus sharp debridement). To address Specific Aim 3 (investigating patient, caregiver, and clinician perceptions of larval therapy dressings and bedside sharp debridement using self-reported assessments, independent samples t-tests will be used to analyze data measured at the interval level, Wilcoxon rank sum tests will be used to analyze data measured at the ordinal level, and chi-square tests (or Fisher exact tests in the case of data sparseness) will be used to analyze categorical data. All hypotheses testing will be two-sided using a level of significance of .05. Data will be analyzed as "intent to treat." SAS version 9.2 (Cary, N.C.) will be used for all analysis.

Data and Safety Monitoring Plan

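### The Aim 1 tissue outcome rests on a provider grade that is probably unblinded, while the planned blinded photo rating feeds no analysis

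*Combined protocol and SAP*

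**What the plan says.** All places are in the Combined protocol and SAP.

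- **Specific Aim 1** lists two comparisons. The first is "The visual reduction of non-viable tissue in the wound bed of chronic full-thickness lower extremity or diabetic foot ulcers". No assessor is named.
- **Methods for Data Collection & Data Management (variable table)** assigns the percentage of non-viable wound tissue to Aim 1, at Day 0 and Day 8, with source "Provider assessment".
- **The opening study summary** has a clinician grade at each visit: "Clinicians will be asked to grade the amount of non-viable tissue apparent in the wound bed". Blinding is not mentioned.
- **Setting, Sample**, at both sites, says that the subject's "wound providers (clinicians) will be the ones to perform the sample collection and apply the LDT or bedside sharp debridement". The sharp debridement (control) procedure likewise assigns debridement to the patient's "wound clinician using standard technique on day 0 after baseline wound measures are obtained and again on day 7".
- **Data Collection & Data Management** plans a separate reading on a 0 to 10 scale: "Photos will be reviewed by blinded wound clinicians and rated on amount of necrotic tissue present visually in wound bed at each sampling time".
- **Data Analysis** states for Aim 1 that "changes (post minus pre) in percent of non-viable tissue and bacterial biofilm will be analyzed using independent samples t-tests". It does not mention the photo rating.

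The photo schedules do not agree. For the larval arm the procedure text says "Wound measurements and wound photos will be taken at baseline and Day 8", while the sampling timeframe also lists a Day 4 photo. The control procedure lists Days 0, 4, 7 and 8. The summary offers Days 0, 4 and 8, or alternatively before and after each debridement.

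**The concern.** How much of a wound bed is non-viable is a matter of visual judgement. The debridement cannot be hidden from the person who applies the larval bag or does the sharp debridement. If that person also supplies the grade, expectations about either method can move the score in one arm more than in the other. A larger sample does not remove that kind of error.

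The stakes are high within this plan. Tissue change is one of two Aim 1 outcomes, and Aim 1 is the aim on which the power analysis rests. The protocol already provides for blinded raters but does not connect their scores to the test that needs them.

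**Working it through.** **1. Which measure the test uses.** Two measures of the same feature are planned.

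| | Provider grade | Photo rating |
|---|---|---|
| Rater | Provider | Blinded wound clinicians |
| Days | Day 0 and Day 8 (table); each visit (summary) | Each sampling time (Days 0, 4, 8) |
| Scale | Percent | 0 to 10 bands |
| Term | Non-viable tissue | Necrotic tissue |
| Listed in the variable table | Yes, under Aim 1 | No |
| Named in Data Analysis | Not by name, but the term and unit match | No |

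The variable tested matches the table row in name and in unit. The row has one day after baseline, Day 8. Read together, the two sections give the Aim 1 tissue test as Day 8 minus Day 0 in the provider grade.

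**2. Whether the provider knows the arm.** The text uses the word provider for the subject's own wound clinicians, and these clinicians debride in both arms. Nothing says that the grader is blinded or is a different person. Knowledge of the arm is therefore probable but not stated.

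**3. The plan's own figure.** Inputs from Sample Size Power Analysis: effect 0.50 SD, two-sided 5%, 80% power. The two-sample t calculation gives 63.77, rounded up to 64 per group, with power 80.1% at 64. The stated figure reproduces.

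**4. Effect of a differential lean (illustration).** Let b be the between-arm difference in grading lean, in SDs of the change score, with no true effect. The t statistic is noncentral with 126 df and noncentrality b × √(64/2) = 5.657b.

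- b = 0.1: noncentrality 0.566, rejection rate 8.7%.
- b = 0.2: noncentrality 1.131, rejection rate 20.2%.

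At assumed SDs of 15, 25 or 35 percentage points, 0.1 SD is 1.5, 2.5 or 3.5 points and 0.2 SD is 3, 5 or 7 points.

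**5. Precision cost of the photo rating.** Rounding to 10-point bands adds a variance of 100/12 per rating, so 2 × 100/12 = 16.7 to a change. An assumed reading error of 5 points SD adds 2 × 25 = 50 more, 66.7 in total. The effective effect is 0.5/√(1 + added variance/SD²).

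| Assumed SD (points) | Bands only: effect | Power | Bands plus reading error: effect | Power |
|---|---|---|---|---|
| 15 | 0.482 | 77.3% | 0.439 | 69.3% |
| 25 | 0.493 | 79.1% | 0.475 | 76.1% |
| 35 | 0.497 | 79.6% | 0.487 | 78.0% |

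The comparator is 80.1% with an error-free measure.

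**6. Availability.** The two procedure sections and the sampling timeframe schedule Day 0 and Day 8 photos in both arms. The timeframe places the Day 0 photo before the first debridement.

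**The case against.** The strongest reply is that the table's provider could be the blinded photo rater, who is also a wound clinician, and that a photo reading fits the visual reduction named in Aim 1. Timing alone does not refute this, because the summary already gives the clinician grade a second schedule. But the text never makes the link. It uses provider for the treating clinicians, the scales differ, and the summary lists the grade beside signs of infection at each visit, which reads as a bedside assessment. The reply shows that one sentence might settle the matter. It does not show that the plan contains that sentence.

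Three further objections stand:

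- The lean, the SDs and the reading error are all assumptions. The power figures also compare the photo rating with a perfect measure. The provider grade has error too, so the real cost of switching may be smaller.
- The fix changes the measure: a percentage of non-viable tissue becomes a banded score of necrotic tissue. The background uses the two terms almost interchangeably, but the plan should say so.
- The summary's alternative schedule would give controls photos around Days 0 and 7 and not clearly at Day 8. Day 8 photos are therefore not guaranteed by every section.

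A reader might infer that the source is wholly open and could be picked after both sets of scores are seen. The documents do not support that reading: taken with the table, Data Analysis points to the provider grade and to Day 8.

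**Conclusion.** The concern holds as a gap between two parts of the plan, and it should be fixed before any ratings are seen. As written, an Aim 1 t-test rests on a subjective grade that was probably made with knowledge of the arm, and the planned blinded rating is used nowhere. A reader might go further and say that the protocol makes the treating clinician the assessor. It does not say so; that step is inferred from who delivers the debridement.

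The absence of the photo rating from the table and the analysis is certain from the text. The size of any bias is unknown. The rates of 8.7% and 20.2% show only what leans of 0.1 and 0.2 SD would do at 64 per arm. The sample size itself is not in dispute.

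**What to change.** - In the table row and in Data Analysis, define the Aim 1 tissue outcome as the change (Day 8 minus Day 0) in the blinded photo rating. Specify the Day 0 photo taken before debridement. List the provider grade as supportive.
- State that the rating of necrotic tissue is taken as the measure of non-viable tissue, and that it is scored in bands of about 10 percentage points.
- Show raters only the sampling-time photos, with arm and day hidden. Day 7 photos exist only in the control arm and would reveal it.
- Reconcile the photo schedules in the summary, the two procedure sections and the sampling timeframe, including the larval-arm Day 4 photo and the Day 8 photo in both arms.

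**Cost.** No new visit, reader or procedure is needed, because the photos and blinded raters are already planned. Against an error-free measure, power at 0.5 SD falls from 80.1% to about 77–80% from banding alone, and to about 69–78% with the assumed 5-point reading error. One limit remains: a recently debrided wound may still hint at the arm, since the control Day 8 photo comes 24 hours after the second sharp debridement.

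### The plan sends treatment information with the wound samples to the laboratories and does not mask them, so the arm can be revealed to those reading biofilm CFU, MMP and IL-6 on Days 4 and 8

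*Combined protocol and SAP*

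**What the plan says.** All references are to the combined protocol and SAP.

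- **What the laboratories receive** (section 6, Data Collection & Data Management, Measurement of bacterial colonization). One sentence defines what may be passed on. It opens "Only de-identified pertinent information per subject sample such as age of subject, visit number (Day 0, 4, 8), location of wound, duration of wound" and ends "co-morbid conditions, medications and current wound treatments will be shared with the investigational laboratories or their personnel".
- **What the tube shows** (Study procedures, Sample Collection). "The sample receptacles will be labeled with assigned subject number, number of visit (1, 2, 3, etc.), date of sample collection", followed by wound duration and location. Treatment is not on the label. Samples go to a VA laboratory; the data collection text also mentions a UF lab. The protocol does not say which of them counts colonies.
- **Stored larvae** (same section, larval group). Larvae from each removed BioBag are labelled with the subject number and the application number, then frozen in the VA research laboratory.
- **Outcomes read in the laboratory.** Specific Aim 1 includes "The reduction in colony forming units (CFU) of bacterial biofilm in samples taken from the wound bed". MMPs and IL-6 belong to Specific Aim 2. Data Analysis tests the Aim 1 outcomes as post-minus-pre changes, compared between arms by independent-samples t-tests.
- **Blinding.** The only statement is "Photos will be reviewed by blinded wound clinicians and rated on amount of necrotic tissue present visually in wound bed". Nothing equivalent is said about the laboratory.

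**The concern.** De-identification hides who the patient is. It does not hide which treatment the patient received. During the study period, a description of the present wound treatment can amount to a statement of the allocation.

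Biofilm CFU is one of two Aim 1 outcomes, and Aim 1 is the basis of the sample size. The protocol describes serial dilution, plating and counting after about 24 hours by standard techniques, and gives no counting rules. Any discretion the reader has is then exercised without protection from knowledge of the arm. A bias introduced at reading cannot be removed in the analysis. Patients and treating clinicians cannot be masked to these two treatments, so masking the laboratory reading is one of the few safeguards available.

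**Working it through.** **Step 1. Does the shared information identify the arm?**

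| Sample | Larval arm | Sharp arm | Does present treatment reveal the arm? |
|---|---|---|---|
| Day 0 | before first BioBag | before first debridement | Not necessarily; study treatment has not begun |
| Day 4 | BioBag, saline gauze | sharp debridement, wound gel | Yes, if study treatment is reported |
| Day 8 | BioBag, saline gauze | sharp debridement, wound gel | Yes, if study treatment is reported |

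Both post-treatment samples are exposed; the baseline sample need not be.

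**Step 2. Is there another route?** Tubes carry the subject number. Larvae from the larval arm carry the same number and are kept in the VA research laboratory, and wound samples also travel to a VA laboratory. If these are the same facility or share staff, a subject number found on a larval container identifies the arm. The documents do not settle whether they are the same.

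**Step 3. Is there a safeguard elsewhere?** The Confidentiality, Sample Collection, Data Collection and Data Analysis sections contain no sample code that conceals the arm, no masked plate reading and no rule withholding treatment until results are final.

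**Step 4. Does visit number matter by itself?** Suppose the reader knows only pre or post status and shifts post readings by *b*. The mean change moves by *b* in both arms, and the between-arm difference moves by *b* − *b* = 0. If the arm is also known, the shifts can differ (*b*₁ and *b*₂), and the difference moves by *b*₁ − *b*₂. Knowledge of the arm is the operative problem.

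**Step 5. The plan's own figure.** Inputs from Sample Size Power Analysis: effect size 0.50, two-sided alpha 0.05, 64 per arm, at least 80% power. For the two-sample t-test, df = 2 × 64 − 2 = 126, the critical value is 1.979, and the noncentrality is d × √(64/2) = 0.50 × 5.657 = 2.828. Power is 80.1%. At 63 per arm it is 79.5%, so 64 is reproduced.

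**Step 6. Illustration of size.** The documents give no figure for reader bias. Assume no true difference and a differential reading shift of d standard deviations of change:

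| Assumed shift d | Noncentrality d × 5.657 | Two-sided rejection rate |
|---|---|---|
| 0 | 0 | 5.0% |
| 0.05 | 0.283 | 5.9% |
| 0.10 | 0.566 | 8.7% |
| 0.20 | 1.131 | 20.2% |
| 0.30 | 1.697 | 39.1% |

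These rates show how sensitive the planned test is to a shift. They do not estimate what will happen in this trial.

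**The case against.** The best defence is that the sentence is a confidentiality limit. It caps what may leave the study folders; it does not say when the information travels, in what form, or that the person counting colonies sees it. The tube label omits treatment. The treatment item could mean background care, since both arms continue provider-ordered wound care and wound treatments are also listed among the health-record data. CFU counts are more objective than visual ratings, and for the ELISA and FRET assays the documents show no reader discretion at all.

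Much of this stands, and it rules out several stronger readings that a reader might infer:

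- **That every sample is read with knowledge of the arm.** The documents do not say the reader consults the information, and the Day 0 sample precedes study treatment.
- **That visit number is itself a source of bias.** Both arms are sampled on the same days, and Step 4 shows that pre/post knowledge without arm cancels.
- **That CFU is the only Aim 1 measure that can be masked.** Non-viable tissue has a blinded photo rating in the text, although the variable table lists its source as provider assessment.
- **That industry funding shows the reading will be slanted.** The laboratories mentioned are VA and UF, and the Conflict of Interest section reports no investigator conflict.

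What does not stand is the suggestion that nothing needs changing. The sentence says the information will be shared, names laboratory personnel as possible recipients, and does not restrict the treatment item to background care. No other text masks the laboratory.

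**Conclusion.** The concern holds as a matter of exposure. The protocol plans a disclosure that can reveal the arm for Day 4 and Day 8 samples to those measuring an Aim 1 outcome and the Aim 2 assays, with a possible second route through the stored larvae and no masking of the laboratory.

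This rests on two assumptions: that the treatment item includes the study debridement and dressing, which is the natural reading but not compelled, and that the information can reach the reader, which the wording allows but does not assert.

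The size of any bias is unknown. The range of about 9% to 39% depends wholly on assumed shifts of 0.1 to 0.3 SD that have no source in the documents; if readers never see the treatment, the rate stays at 5%. This should be fixed because the remedy is cheap and the loss cannot be repaired once samples are read. The evidence does not show that the outcome is compromised.

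**What to change.** 1. In Data Collection & Data Management, remove the treatment item from what the laboratories receive until CFU, MMP and IL-6 results are locked. Check that the medications field does not disclose the arm.
2. Label wound samples with a coded sample number in place of the subject number. Do not use that code on the stored larvae. The study coordinator holds the key.
3. State in the protocol that laboratory readers are masked to arm until results are locked, and name the laboratory that counts CFU.
4. Masking visit number and collection date is optional.

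The cost is a short text change, coded labels and a linkage log kept across the two sites, with some added risk of mislabelling that the log must control. Sample size, visits, procedures and patient care do not change, and the planned correlation of larval and wound bacteria remains possible through the key.
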